12.1 Subgroup Analyses of Efficacy

If there are enough patients per group, subgroup analyses may be evaluated for any potential impact of demographics or baseline disease characteristics on the efficacy endpoints. Subgroups may include, but are not limited to, baseline hemoglobin (< 100 g/L vs. ≥ 100 g/L), and baseline platelet count ($\leq 50,000/\mu\text{L}$ vs. $> 50,000/\mu\text{L}$).

13 SAFETY ANALYSES

Safety analyses include summaries and graphical presentations of treatment emergent adverse events, clinical labs, ECG, vital signs, performance status, and any abnormal findings observed during the performance of physical examinations by treatment received after randomization through the end of assigned study treatment + 30 days.

The primary safety measure for dosage selection is the percentage of patients with CTCAE grade 3/4 cardiac treatment-emergent AEs, CTCAE grade 3/4, hemorrhage treatment-emergent AEs, CTCAE grade ≥ 4 thrombocytopenia toxicity, or CTCAE grade ≥ 4 anemia toxicity. Cardiac and hemorrhage treatment-emergent AEs will be determined using Standardized MedDRA Query (SMQ). See section 9.1 for more details. Thrombocytopenia and anemia will be determined by central laboratory measurement.

All other safety data including TEAEs, death, and clinical laboratory measures will be used as supportive measures for evaluation of pacritinib dose-safety relationship.

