Serum chemistry parameters (ALT/SGPT and AST/SGOT, alkaline phosphatase, bilirubin [total, direct, and indirect], creatinine, LDH, sodium, potassium, chloride, bicarbonate, calcium, phosphate, magnesium, BUN/urea, albumin, amylase, lipase, glucose, cholesterol, uric acid, and high sensitivity CRP) will be evaluated by a central laboratory at screening, baseline, and as clinically indicated and will include measures of hepatic and renal function and dysfunction. Blood samples drawn at unscheduled visits for serum chemistry evaluation should be submitted to the central laboratory for assessment in addition to any local laboratories needed for timely decisions regarding patient care. Pacritinib dosage modifications will be implemented for clinically significant AEs identified with this testing per the stated guidelines for "Pacritinib-

	Related Nonhematologic Toxicities Other than QTc Prolongation, Decreased Cardiac Ejection Fraction, or Diarrhea".
Pacritinib Dosage Modifications	Pacritinib dosage may be interrupted or modified for hematologic toxicities, hemorrhage, severe infections, cardiac toxicities including QTc interval prolongation and reduction in ejection fraction, diarrhea, and other pacritinib-related nonhematologic toxicities. Pacritinib dosage may also be held for invasive procedures. Refer to Section 6.5 for pacritinib dosage management guidelines.

STATISTICAL METHODS

The following variables will be used to evaluate efficacy and safety.

Efficacy

- The primary efficacy variable for dosage selection is the percent reduction in spleen volume from baseline as measured by MRI or CT at Weeks 12 and 24.
- Other supportive measures for evaluation as part of the dose-response relationship include: the percentage of patients who achieve at least 35% reduction in spleen volume; % TSS reduction from baseline; and the percentage of patients with at least 50% reduction in TSS.

Safety

- The primary safety measure for dosage selection is the percentage of patients with CTCAE grade ≥3 cardiac AEs (Standardized MedDRA Query [SMQ]), CTCAE grade ≥3 hemorrhage AEs (SMQ), CTCAE grade ≥4 thrombocytopenia toxicity (central laboratory based), or CTCAE grade ≥4 anemia toxicity (central laboratory based).
- All other safety data including AEs, death, and clinical laboratory measures will be used as supportive measures for evaluation of pacritinib dose-safety relationship.

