The incidence of TEAEs in the SMQ hemorrhages was similar during treatment with pacritinib (33.7%) and BAT (30.4%) in the PERSIST-1/-2 studies. However, the incidence of hemorrhage events was lower in the 400 mg QD arm compared to the 200 mg BID arm for all categories of TEAEs, including SAEs. The most common bleeding events were epistaxis, contusion, hematoma and GI hemorrhage and these events occurred at a similar frequency to patients treated with BAT. Importantly, one of the most common TEAEs in the "watch and wait only" patients was epistaxis (26.3%), indicating a baseline level of bleeding without any therapy, in this MF population. Most events in the SMQ hemorrhages were low grade, however, severe and sometimes life-threatening and fatal hemorrhagic events have been reported across the PERSIST-1/-2 studies. These outcomes comprised predominantly GI bleeding (including gastric variceal hemorrhage, melena, and esophageal hemorrhage) and intracranial hemorrhage, cerebral hemorrhage and meningorrhagia. Overall, hemorrhagic TEAEs resulted in death in seven patients in the PERSIST-1/-2 studies, two treated with pacritinib 200 mg BID, four treated with pacritinib 400 mg QD, and one after crossover from BAT to pacritinib.

The incidence of a new hemorrhage event TEAE was highest at the start of treatment and then diminished with continued treatment in all treatment groups. Serious hematological events occurred in patients with complicated medical histories, severe comorbidities, concomitant antiplatelet use, and myelosuppression. The risk of bleeding episodes did not appear to be related to the degree of thrombocytopenia.

Diarrhea

Patients in the PERSIST-1/-2 studies were evaluated at baseline to assess usual bowel habits and instructed on the need for early intervention for possible GI adverse effects associated with treatment. During each study, standard supportive care measures were provided to control symptoms of GI toxicity.

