11.1 Variables for the Analysis

Efficacy

- The primary efficacy variable for dosage selection is the percent reduction in spleen volume from baseline as measured by MRI (preferred) or CT at Weeks 12 and 24.
- Other supportive measures for evaluation as part of the dose-response relationship include: the percentage of patients who achieve at least 35% reduction in spleen volume; % TSS reduction from baseline; and the percentage of patients with at least 50% reduction in TSS.
- Long term efficacy is evaluated using percent reduction in spleen volume from baseline as measured by MRI or CT, percent reduction in TSS from baseline, percent reduction in spleen length by physical exam and the patient global impression assessment.

Safety

- The primary safety measure for dosage selection is the percentage of patients with CTCAE grade ≥3 cardiac AEs (Standardized MedDRA Query [SMQ]), CTCAE grade ≥3 hemorrhage AEs (SMQ), CTCAE grade ≥4 thrombocytopenia toxicity (central laboratory based), or CTCAE grade ≥4 anemia toxicity (central laboratory based).
- All other safety data including AEs, death, and clinical laboratory measures will be used as supportive measures for evaluation of pacritinib dose-safety relationship and for long term safety evaluation.

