13.1 ADVERSE EVENTS

Treatment-emergent AEs (TEAEs) will be summarized by presenting, for each treatment arm, the count and percentage of patients having any TEAE, having a TEAE in each body system, and having an individual event according to version 16.0 of the MedDRA dictionary. CTCAE (version 4.03) grades and relationship to study medication will be summarized as appropriate. For summaries by CTCAE grade or relatedness, only the highest CTCAE grade or degree of relatedness of each SOC and/or preferred term will be summarized. A patient having the same event more than once will be counted only once and by greatest severity or closest relationship.

In addition, serious TEAEs (SAEs), CTCAE grade 3 or 4 TEAEs, TEAEs leading to study medication discontinuation, interruption, or dose reduction, TEAEs with an outcome of death, and related TEAEs will be summarized. A listing of all SAEs will be generated. The preferred term of TEAEs of all grades, as well as for TEAEs of grade 3 or 4 will also be presented for each treatment arm by decreasing frequency in the PAC 200 mg BID arm.

Cardiac, hemorrhage, skin neoplasms, and hypersensitivity TEAEs as defined by Standardised MedDRA Queries (SMQs) will also be summarized by SOC and preferred term. Cardiac TEAEs are all the preferred terms in the SMQs of Cardiac Arrhythmias, Cardiac Failure, Ischaemic Heart Disease, and Embolic and Thrombotic Events. Hemorrhage TEAEs are all preferred terms in the SMQ of Haemorrhages. Skin neoplasm TEAEs are all preferred terms in the SMQ of Skin Neoplasms (malignant and unspecified). Hypersensitivity TEAEs are all preferred terms in the SMQ

of Hypersensitivity. A listing of time to onset and resolution of these TEAEs will also be presented by treatment arm. These will also be presented graphically.

The counts and percentages for the causes of all deaths will be presented by treatment arm. A listing of all deaths, both on and off treatment, will also be generated. On treatment deaths are defined as deaths that occur on treatment and within 30 days of treatment discontinuation.

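### The SAP narrows the primary safety measure from grade ≥3 to grade 3/4 cardiac and hemorrhage events; read literally, a patient whose only qualifying event is fatal is not counted

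*SAP*

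**What the plan says.** The protocol defines the primary safety measure for dosage selection twice, in the synopsis (Statistical Methods, Safety) and in section 11.1, and the two agree. The event components are "CTCAE grade ≥3 cardiac AEs (Standardized MedDRA Query [SMQ"]) and "CTCAE grade ≥3 hemorrhage AEs (SMQ"). The other two components are central-laboratory thrombocytopenia and anemia of grade ≥4. A patient counts if any one component is met.

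SAP section 13 gives a measure of the same name and purpose as the "percentage of patients with CTCAE grade 3/4 cardiac treatment-emergent AEs, CTCAE grade 3/4, hemorrhage treatment-emergent AEs", and keeps the ≥4 notation for the two laboratory components in the same sentence. It continues: "All other safety data including TEAEs, death, and clinical laboratory measures will be used as supportive measures". For the event definitions it says "See section 9.1 for more details".

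SAP section 13.1 lists among the planned summaries "CTCAE grade 3 or 4 TEAEs, TEAEs leading to study medication discontinuation, interruption, or dose reduction, TEAEs with an outcome of death". For summaries by grade or relatedness, "only the highest CTCAE grade or degree of relatedness of each SOC and/or preferred term will be summarized".

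**The concern.** Grade ≥3 covers grades 3, 4 and 5; grade 3/4 does not cover grade 5. Grade 5 is in use for these events: protocol section 2.2 sends grade 4 and grade 5 cardiac and bleeding events to the adjudication committee. Someone programming from the SAP would probably code grades 3 and 4 only, and a patient whose sole qualifying event was a fatal bleed or fatal cardiac event would then be recorded as free of the primary safety outcome.

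This measure is meant to inform the choice of dose, which is the trial's primary objective. Fatal intracranial hemorrhage, cardiac failure and cardiac arrest were among the concerns behind the clinical hold described in protocol section 1.3.4. The error runs one way: it removes the gravest outcomes and can only make an arm look safer. If fatal events differ by dose, it would also flatten the dose-safety relationship that the trial sets out to describe.

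**Working it through.** **1. The definitions side by side**

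| Component | Protocol synopsis and 11.1 | SAP 13 |
|---|---|---|
| Cardiac (SMQ) | grade ≥3 | grade 3/4 |
| Hemorrhage (SMQ) | grade ≥3 | grade 3/4 |
| Thrombocytopenia (central lab) | grade ≥4 | grade ≥4 |
| Anemia (central lab) | grade ≥4 | grade ≥4 |

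Only the two event components differ. Both notations stand in one SAP sentence, which makes it harder to read 3/4 as loose shorthand for ≥3. The SAP's table of modifications records many changes but not this one, and no other SAP text puts grade 5 back into the measure.

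**2. Who drops out**

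The measure is a patient-level composite joined by *or*. A patient with a fatal event still counts if another component is met, such as a separate grade 3 or 4 event or grade ≥4 laboratory thrombocytopenia. The patient lost is the one whose only qualifying event is grade 5.

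The loss would be wider if the highest-grade rule of SAP 13.1 governed this measure, because a grade 3 or 4 event that became fatal under the same term would be carried at grade 5 and fall outside 3/4. The SAP does not say whether it does. The pointer to section 9.1 does not help: SAP section 9 covers drug exposure and has no 9.1.

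**3. Size per omitted patient**

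- 50 per arm (protocol 11.7): 1/50 = 2.0 percentage points.
- 35 per arm (SAP 16): 1/35 = 2.9 percentage points.

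**4. How often it could arise**

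The plan gives no figure for this measure. The nearest is in protocol 11.7, the chance of seeing at least one event in 50 patients at a true rate of 5%: 1 − 0.95^50 = 92.3%, against 92% stated. It reproduces, and the same formula is used below.

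Protocol section 1.3.4 reports that "hemorrhagic TEAEs resulted in death in seven patients in the PERSIST-1/-2 studies, two treated with pacritinib 200 mg BID". The 200 mg BID denominator in the same pooled studies is 106 (48/106 is given for related grade 3/4 AEs). So p = 2/106 = 1.89%, with exact (Clopper-Pearson) 95% interval 0.23% to 6.65%. *Assumption: this rate applies to an arm of the present trial.*

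P(at least one fatal hemorrhage) = 1 − (1 − p)^n:

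| n | p = 0.23% | p = 1.89% | p = 6.65% |
|---|---|---|---|
| 50 | 11% | 61% | 97% |
| 35 | 8% | 49% | 91% |

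These are upper figures for an omitted patient from this cause, since some would qualify through another component. As an illustration only, if half had no other qualifying event, the 50-patient figure is 1 − (1 − p/2)^50 = 38% (6% to 82%).

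No cardiac figure is given. Protocol 1.3.4 reports no fatal cardiac disorder TEAEs on 200 mg BID, and that grouping is not the four-SMQ cardiac set defined in SAP 13.1.

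**The case against.** The strongest reply is that the text proves an inconsistency, not that fatal cases will be dropped. Protocol section 11 says it sets out the methodology for the primary safety endpoint and leaves supportive analyses to the SAP, and SAP section 1 describes itself as adding detail. On that view the protocol definition governs and the SAP wording is a slip. Likewise, listing grade 3 or 4 events apart from deaths in SAP 13.1 follows protocol 11.6, where it coexists with a grade ≥3 primary measure. Both points are fair. They weaken any inference about intent, but programs are written from the SAP, and its text says 3/4.

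The highest-grade rule is addressed to summaries by grade or relatedness, so it may never have been meant for a patient-level composite. That is why the point is conditional here.

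The probabilities rest on thin data. Two deaths on 200 mg BID say nothing direct about the two lower-dose arms, exposure time is not matched, and entry criteria here restrict recent bleeding. The intervals are very wide and the one-half scenario has no source. This stands: only the 2.0 or 2.9 points per patient is firm.

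The practical consequence is also limited. No hypothesis is tested, no threshold is set on this percentage, and selection also draws on efficacy, dose-response and PK/PD. Fatal events remain visible: the IDMC trigger is grade ≥4, the adjudication committee reviews grades 4 and 5, and SAP 13.1 tabulates fatal TEAEs and causes of death by arm. The protocol, like the SAP, treats death as supportive. None of this repairs the primary percentage. Under the protocol, fatal cardiac and hemorrhage events enter it through grade ≥3; under the SAP wording they do not.

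**Conclusion.** The concern holds as a discrepancy between the protocol and the SAP in the definition of the primary safety measure, and the discrepancy is unexplained. Followed literally, the SAP understates the measure by 2.0 points (50 per arm) or 2.9 points (35 per arm) for each patient whose only qualifying event is fatal. On the assumption that the earlier 200 mg BID fatal hemorrhage rate carries over, at least one fatal hemorrhage in a 50-patient arm is plausible (61%, range 11% to 97%), and the chance of an omission from this cause is no higher than that. The true rate may be lower. The documents do not show that the dose chosen would differ. What is established is that the reported primary safety percentage would not be the one the protocol defines. It should be fixed before analysis.

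**What to change.** In SAP section 13, restore CTCAE grade ≥3 for both the cardiac and the hemorrhage components, matching protocol 11.1. Add one sentence saying that a patient is counted once if any qualifying cardiac or hemorrhage event is grade 3, 4 or 5, and that the highest-grade display rule in 13.1 never removes a patient from this measure. Redirect the section 9.1 pointer to 13.1, where the SMQs are listed. If the narrower range was intended, the table of modifications should say so and give the reason.

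The cost is one or two lines of SAP text and one condition in the derivation. No new data are needed. The reported percentage may become slightly less favourable.

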13.1 ADVERSE EVENTS

Treatment-emergent AEs (TEAEs) will be summarized by presenting, for each treatment arm, the count and percentage of patients having any TEAE, having a TEAE in each body system, and having an individual event according to version 16.0 of the MedDRA dictionary. CTCAE (version 4.03) grades and relationship to study medication will be summarized as appropriate. For summaries by CTCAE grade or relatedness, only the highest CTCAE grade or degree of relatedness of each SOC and/or preferred term will be summarized. A patient having the same event more than once will be counted only once and by greatest severity or closest relationship.

In addition, serious TEAEs (SAEs), CTCAE grade 3 or 4 TEAEs, TEAEs leading to study medication discontinuation, interruption, or dose reduction, TEAEs with an outcome of death, and related TEAEs will be summarized. A listing of all SAEs will be generated. The preferred term of TEAEs of all grades, as well as for TEAEs of grade 3 or 4 will also be presented for each treatment arm by decreasing frequency in the PAC 200 mg BID arm.

Cardiac, hemorrhage, skin neoplasms, and hypersensitivity TEAEs as defined by Standardised MedDRA Queries (SMQs) will also be summarized by SOC and preferred term. Cardiac TEAEs are all the preferred terms in the SMQs of Cardiac Arrhythmias, Cardiac Failure, Ischaemic Heart Disease, and Embolic and Thrombotic Events. Hemorrhage TEAEs are all preferred terms in the SMQ of Haemorrhages. Skin neoplasm TEAEs are all preferred terms in the SMQ of Skin Neoplasms (malignant and unspecified). Hypersensitivity TEAEs are all preferred terms in the SMQ

of Hypersensitivity. A listing of time to onset and resolution of these TEAEs will also be presented by treatment arm. These will also be presented graphically.

The counts and percentages for the causes of all deaths will be presented by treatment arm. A listing of all deaths, both on and off treatment, will also be generated. On treatment deaths are defined as deaths that occur on treatment and within 30 days of treatment discontinuation.

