1.2 Myelofibrosis

1.2.1 Clinical Presentation and Disease-Related Symptoms

MF may present as either a primary myeloproliferative disorder or follow a diagnosis of PV or ET. Regardless of the original diagnosis, PMF, post-polycythemia vera MF (PPV-MF), and post-essential thrombocythemia MF (PET-MF) have a common pathophysiological profile, characterized by elevated numbers of CD34-positive cells in the marrow in the early phase of the disease, followed in the later phases by marrow fibrosis, with decreasing numbers of CD34 cells in the marrow and a corresponding increase in splenic and liver engorgement by CD34 cells.

PMF, PPV-MF and PET-MF usually present with a white blood cell (WBC) count <30,000/mm³, prominent teardrops on peripheral smear, normocellular or hypocellular marrow with moderate to marked fibrosis, an absence of the Philadelphia chromosome or the BCR-ABL translocation, and frequent positivity for the *JAK2* mutation (Campbell and Green 2006). In addition to the clonal proliferation of a multipotent hematopoietic progenitor cell, an event common to all chronic MPDs, these disorders are characterized by colonization of extramedullary sites, such as the spleen or liver (Barosi 1999, Tefferi 2000).

About 70% of patients with MF are symptomatic at presentation. The main physical findings are splenomegaly and hepatomegaly. Other symptoms include those secondary to a hypercatabolic state (fever, weight loss, and night sweats) and peripheral blood abnormalities (fatigue and dyspnea resulting from anemia and bleeding; petechiae resulting from thrombocytopenia and/or abnormal platelet function). Gout and renal stones secondary to hyperuricemia are also common (Ahmed and Chang 2006). Other clinical manifestations of the disease include thromboembolic episodes, hemorrhage, splenic pain, early satiety, anemia, and bone pain.

PMF, PPV-MF, and PET-MF have similar types and distributions of bone marrow cytogenetic abnormalities (Tefferi et al 2001), and they are known to harbor a common mutant allele, *JAK2V617F* (James et al 2005).

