While many patients had stable or increasing platelet counts during treatment, some decreases were observed. The incidence of the TEAE of thrombocytopenia was higher during treatment with pacritinib (27.9%) than with BAT (18.6%) in the PERSIST 1/-2 studies. The incidence of thrombocytopenia was generally higher in the 200 mg BID arm compared to the 400 mg QD arm. This was true for all TEAEs (34.0% vs. 25.9%, respectively), related TEAEs (20.8% vs. 16.0%), grade 3/4 TEAEs (21.0% vs. 32.1%), and SAEs (1.9% vs. 5.7%).

Despite thrombocytopenia, most pacritinib patients continued treatment without dose modification. Overall, only 2.5% of patients on 400 mg QD and 1.9% on 200 mg BID, discontinued due to thrombocytopenia and only 2.8% on 400 mg QD and 1.9% on 200 mg BID, had a dose reduction due to thrombocytopenia. In patients with a platelet count below $100,000/\mu$ L, only 4.0% of patients on 400 mg QD and 1.9% of patients on 200 mg BID, discontinued due to thrombocytopenia. For those who had dose modifications due to thrombocytopenia, dose reduction or short term interruption allowed treatment continuation. Importantly, treatment emergent thrombocytopenia or worsening of baseline

thrombocytopenia did not appear to be associated with treatment-emergent AEs of bleeding. Hemorrhagic events were reported in pacritinib treated patients with or without severe thrombocytopenia.

Anemia

The TEAE of anemia was higher during treatment with pacritinib (28.1%) than with BAT (17.6%) in the PERSIST-1/-2 studies. However, the incidence of anemia was generally lower in the pacritinib 200 mg BID arm compared to the 400 mg QD arm. This was true for all TEAEs (23.6% vs. 29.6%, respectively), related TEAEs (13.2% vs. 17.9%), grade 3/4 TEAEs (21.7% vs. 26.2%), and TEAEs leading to dose reduction (0.9% vs. 3.7%).

Mean (SD) baseline hemoglobin levels for the 400 mg QD and 200 mg BID arms were 103.9 (23.3) g/L and 98.9 (22.0) g/L, respectively, indicating in general, patients were anemic at study entry.

Hemorrhage

Patients with MPNs are at increased risks for thrombosis and major bleeding. Hemorrhagic events have been reported in pacritinib-treated patients with and without severe thrombocytopenia.

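### The SAP's definition of a cardiac event takes in every embolic and thrombotic term, so the cardiac component of the primary safety measure, and with it the cardiac rate by dose, is mislabelled.

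*SAP*

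**What the plan says.** Protocol 11.1 sets the measure: "The primary safety measure for dosage selection is the percentage of patients with CTCAE grade ≥3 cardiac AEs", together with severe hemorrhage, thrombocytopenia and anemia. It says that cardiac events are found by SMQ but names no SMQ.

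SAP 13 repeats the measure with a slightly different grade range: "The primary safety measure for dosage selection is the percentage of patients with CTCAE grade 3/4 cardiac treatment-emergent AEs". It adds: "Cardiac and hemorrhage treatment-emergent AEs will be determined using Standardized MedDRA Query (SMQ". It then points to section 9.1 for details. SAP 9 covers exposure to study treatment, so the pointer is outdated. The only SMQ list in the SAP is in 13.1, and there the definition reads: "Cardiac TEAEs are all the preferred terms in the SMQs of Cardiac Arrhythmias, Cardiac Failure, Ischaemic Heart Disease, and Embolic and Thrombotic Events".

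Nothing in SAP 13.1 limits the fourth SMQ to cardiac, coronary or arterial sites, and neither document gives a reason for including it. Skin neoplasms and hypersensitivity each get their own SMQ group in SAP 13.1. Embolic and thrombotic events do not. Protocol 11.6 also plans cardiac summaries by SMQ group, overall and by 8-week interval, so the label carries into those tables too.

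**The concern.** A dose-selection reader takes a cardiac rate to mean cardiac events. Under SAP 13.1 it also includes patients whose only qualifying event is a clot elsewhere in the body. Such events are to be expected in this population. Protocol 1.2.1 states "Other clinical manifestations of the disease include thromboembolic episodes, hemorrhage, splenic pain, early satiety, anemia, and bone pain", and protocol 1.3.4 states "Patients with MPNs are at increased risks for thrombosis and major bleeding".

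The label matters because protocol 1.3.4 names cardiac failure and cardiac arrest among the concerns behind the earlier clinical hold, and protocol 2.2 asks the IDMC to focus on bleeding, cardiac events and deaths. If the cardiac figure mixes two kinds of event, nobody can tell from the primary measure whether a difference between doses is cardiac, thrombotic or both. The mislabelling holds however thrombosis behaves. Unrelated to dose, it raises every arm. Falling with dose, it can mask a cardiac increase. Rising with dose, it is reported as cardiac toxicity.

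**Working it through.** **The plan's own figures.** No stated figure depends on the cardiac definition. The nearest are the safety-precision statements, and both reproduce. For protocol 11.7 (50 per arm, 5% event rate, stated 92%), 1 − 0.95^50 = 0.923. For SAP 16 (30 per arm, stated 78%), 1 − 0.95^30 = 0.785. Neither bears on this point.

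**Inputs.**
- Cardiac rate c = 3.8%: grade 3/4 cardiac disorders at 200 mg BID in the pooled Phase 3 studies (protocol 1.3.4, Cardiac Toxicities). It is used only as a plausible base rate.
- Thrombosis rate t: not in the documents. Assumed to be 1%, 2% or 4% of patients with a grade 3/4 non-cardiac thrombosis, the same in every arm and independent of cardiac events.
- Arm size: 50 (protocol 11.7).

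**Effect on the cardiac component.** Rate as counted = 1 − (1 − c)(1 − t). Share with no cardiac event = (rate as counted − c) ÷ rate as counted.

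| t | Calculation | Rate as counted | Share with no cardiac event | Expected patients per 50 |
|---|---|---|---|---|
| 0 | c | 3.8% | 0% | 1.9 |
| 1% | 1 − 0.962 × 0.99 | 4.8% | 20% | 2.4 |
| 2% | 1 − 0.962 × 0.98 | 5.7% | 34% | 2.9 |
| 4% | 1 − 0.962 × 0.96 | 7.6% | 50% | 3.8 |

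The addition is 0.5 to 1.9 patients per arm of 50. From the 8.6% seen at 400 mg QD, the rate as counted would be 1 − 0.914 × 0.99 = 9.5% to 1 − 0.914 × 0.96 = 12.3%, and the share with no cardiac event 10% to 30%.

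**Effect on a dose contrast.** Assume true cardiac rates of 2% and 6% at two doses. The difference as counted is (0.06 − 0.02)(1 − t).

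| t | Lower dose | Higher dose | Difference (points) | Ratio |
|---|---|---|---|---|
| 0 | 2.00% | 6.00% | 4.00 | 3.00 |
| 1% | 2.98% | 6.94% | 3.96 | 2.33 |
| 2% | 3.96% | 7.88% | 3.92 | 1.99 |
| 4% | 5.92% | 9.76% | 3.84 | 1.65 |

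The ratio falls, but the difference hardly moves.

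**Effect on the full composite.** The documents give no composite rate. Assume p = 20% to 40% without thrombosis. The increase is t(1 − p), from 0.01 × 0.60 = 0.6 points to 0.04 × 0.80 = 3.2 points. Patients counted only for thrombosis would then be 0.6 ÷ 40.6 = 1.5% to 3.2 ÷ 23.2 = 14% of the composite, against 20% to 50% of the cardiac component.

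**The case against.** The case for leaving the definition alone has several parts.

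- **A disease feature is not a reason to exclude.** The sentence in protocol 1.2.1 lists hemorrhage and anemia beside thromboembolic episodes, and both stay in the measure. Concurrent randomized arms deal with background events. This stands. A reader might infer that thrombosis should be dropped because the disease causes it, but the documents do not support that. The objection is to the label.
- **The dose comparison survives.** The plan tests no hypothesis and reports percentages by arm, and a dose-independent background leaves the absolute difference almost intact. This also stands. A reader might infer from the falling ratio that the definition hides a dose effect, but that does not follow.
- **Thromboses can be seen elsewhere.** SAP 13.1 tabulates SMQ-defined events by system organ class and preferred term. This helps only in part. A patient can appear under several terms, so these tables do not give the number of patients who meet the composite without the fourth SMQ.
- **The SMQ terms are not in the documents.** That non-cardiac clots are covered is read from the SMQ's unrestricted name and the word *all*. This is a fair limit. The plan contains nothing that narrows it.
- **A late change to a safety component can look data-driven.** The trial is open-label, and an interim analysis was done on 29 June 2018 (protocol 11.8). This stands against removing thrombosis outright, but not against showing both versions.

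**Conclusion.** The point holds as one of labelling and reporting. As written, the plan counts a non-cardiac grade 3/4 thrombosis as a cardiac event in the primary safety measure. At assumed rates of 1% to 4%, unrelated to dose and independent of cardiac events, a 3.8% component would read 4.8% to 7.6%, and 20% to 50% of the patients counted would have had no cardiac event. The true size is unknown because the documents give no thrombosis rate. The effect on the absolute dose difference is negligible under the same assumptions, and the relative effect on the composite is smaller than on the component. The step from SAP 13 to the list in 13.1 is an inference, though a safe one, since there is no other SMQ list in the SAP.

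Two further readings are tempting but not supported:

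- **Two severe clots would suspend enrollment as a cardiac signal.** Protocol 11.9 does not say which definition its trigger on two grade ≥4 cardiac events uses. The adjudication committee and the IDMC also review the nature of each event, and any arm-closure recommendation is non-binding. What can be said is that the definition is left open.
- **Dropping the fourth SMQ would make the rate comparable with the Phase 3 figures.** Protocol 1.3.4 reports cardiac disorders, and nothing shows that the other three SMQs match that grouping.

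**What to change.** 1. In SAP 13.1, report cardiac events by the Cardiac Arrhythmias, Cardiac Failure and Ischaemic Heart Disease SMQs, and report Embolic and Thrombotic Events as its own SMQ group.
2. In SAP 13, present the primary safety measure with and without the Embolic and Thrombotic Events SMQ, and label the wider version *cardiac/thromboembolic*.
3. Correct the pointer in SAP 13 from section 9.1 to 13.1.
4. State which cardiac definition the trigger in protocol 11.9 uses, so that it and SAP 13.1 are reconciled.

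The cost is one extra table, one extra row and a few sentences. All the data are already collected, and showing both versions loses nothing. The SAP's list of modifications should record that the change was made after the June 2018 interim analysis, so that it does not appear to have been chosen on the results.
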